Stratification factor: The stratification factor average weekly frequency of moderate to severe HFs (including nighttime HFs) (see Section 1.2) will be assigned in the IRT system during randomization. The average weekly frequency of moderate to severe HFs is based on HFDD data and will be calculated using the 14 days prior to the visit confirmation date for HF eligibility check. A minimum of 11 days should be available for the calculation of the average weekly value. In case participants are incorrectly stratified, the actual stratification will be used in the analysis. The actual average weekly frequency of moderate to severe HFs will be the value calculated in the eDiary/electronic handheld device. If more than 10% of

Version 2.0 Page: 18 of 57

participants are incorrectly stratified, a sensitivity analysis may be performed using the assigned strata.

Study day 1: Defined as the day of start of treatment, or randomization day if participant did not take study treatment.

Study day: Study day will be calculated using study day 1 as the reference starting day. For observations on or after study day 1, the below formulae will be used:

Study day = date of observation – date of study day 1 + 1

For observations before study day 1, the formulae below will be used:

Study day = date of observation - date of study day 1

Study week: Study week will be calculated for study day >0 using the below formulae:

CEIL is a function in SAS that round up the value to the nearest integer. The calculation would follow the schedule of activities in the protocol (see Section 1.3 in protocol) where day 29 and day 85 with a plus 7-day visit window are specified for week 4 and 12 respectively. This would therefore calculate study day 1 to 7 as study week 0.

Time to event: The start date of treatment for treated participants or the randomization date for randomized participants who did not take study treatment will be used as the start date for the calculation of time to event. Therefore, the time of event will be defined as "date of event – start of treatment date (for treated participants) / randomization date (for randomized but not treated participants) +1".

Unscheduled assessments: Extra assessments (e.g., laboratory data or vital signs) associated with non-protocol visits will be included in listings, but not in the summary tables, unless otherwise specified.

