For the analysis, weekly mean values will be used. The mean daily value for each study week will be calculated by using available data during that week as:

For a particular parameter:

total value of the parameter during that week

total number of available days with morning data for that parameter during that week

Study week will be assigned using the definition in Section 4.1.2 using diary day as the date of observation. Data entered on the morning after the start date of treatment / randomization date will not be used in the calculation of baseline value but will be considered post-baseline.

The mean daily value can be derived if a value is provided for at least 4 out of 7 days with morning data, otherwise the value will be set as missing. The baseline value will be calculated similarly using all available days with morning data during the 14 days prior to starting treatment. A minimum of 7 days should be available for the derivation of the baseline value. Only diary days outside of the impact duration of prohibited hormonal therapies and medication potentially confounding efficacy will be included in baseline derivation. Details regarding the prohibited medications together with the impact duration are described in Section 6.3.

The mean daily value and change from baseline in mean daily value for each parameter will be analyzed using descriptive statistics by study treatment and week. The change from baseline over time by study treatment will be shown using line plots for means and 95% CI.

In addition, the mean daily value from the PSG nights will be summarized descriptively by study treatment and week. The mean value will be calculated using the same rule to calculate the primary endpoint (Section 4.2.1), i.e., if there are sleep diary data for both PSG nights, the mean value of the 2 nights will be used; if only 1 night is available, data from that one night will be used.

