4.4.3 Hot Flash Daily Diary (HFDD)

- Frequency of HFs as measured by HFDD over time
- Change from baseline in proportion of days with participants rating "quite a bit" or "very much" sleep disturbance due to HF as measured by HFDD over time

Participants' assessments of HFs will be recorded electronically twice daily using the sponsor developed HFDD. The HFDD is completed in the morning after waking up (morning diary) and each evening at bedtime (evening diary) on the hand-held device. The HFDD assess the number of mild, moderate, and severe HFs experienced during the day (evening diary) and during the night (morning diary). Therefore, a diary day consists of the evening entry and the morning entry of the subsequent day.

Version 2.0 Page: 31 of 57

Mild HFs are defined as a "sensation of heat without sweating", moderate HFs are defined as a "sensation of heat with sweating, but able to continue activity", and severe HFs are defined as a "sensation of heat with sweating, causing cessation (stopping) of activity".

The following daily HF assessments will be aggregated to a mean daily frequency for each study week:

- moderate to severe nighttime HFs (morning diary)
- mild, moderate, and severe nighttime HFs (morning diary)
- moderate to severe HFs (morning and evening diary)
- mild, moderate, and severe HFs (morning and evening diary)

The mean daily frequency of moderate to severe nighttime HFs for a study week will be calculated as

total number of nighttime moderate to severe HFs during that week total number of available days with morning data during that week

The calculation of mild, moderate, and severe nighttime HFs, moderate to severe HFs and mild, moderate, and severe HFs will be calculated similarly to the above.

Study week will be assigned using the definition in Section 4.1.2. using the diary day as the date of observation. Data entered on the morning after the start date of treatment / randomization date will not be used in the calculation of baseline value but will be considered post-baseline for nighttime HFs. For the mean daily frequency using both the morning and evening diary (i.e., moderate to severe HFs and mild, moderate, and severe HFs), diary day 2 - 8 will be used for week 0.

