A minimum of 4 days should be available within a study week for the derivation of mean daily frequency, otherwise it will be set to missing for that week. The baseline value will be calculated similarly using all available days with data during the 14 days prior to starting treatment. A minimum of 7 days should be available for the derivation of the baseline value. Only diary days outside of the impact duration of prohibited hormonal therapies and medication potentially confounding efficacy will be included in baseline derivation. Details regarding the prohibited medications together with the impact duration are described in Section 6.3.

A day would be considered as available if morning entry (of the subsequent day) is available when only morning diary is used, or if either evening entry or morning entry (of the subsequent day) is available when both evening and morning diaries are used.

The relationship between the frequency of HFs and WASO as measured by PSG will be explored. The PSG value as defined in Section 4.2.1 will be used in the analysis. Scatterplots showing the below will be produced separately for the actual values, change from baseline and percent change from baseline:

- mean daily frequency of moderate to severe nighttime HFs against WASO as measured by PSG
- mean daily frequency of mild, moderate and severe nighttime HFs against WASO as measured by PSG

Version 2.0 Page: 32 of 57

- mean daily frequency of moderate to severe HFs against WASO as measured by PSG
- mean daily frequency of mild, moderate and severe HFs against WASO as measured by PSG

The mean daily HFs for the same week the week 4 and week 12/EoT PSG assessments fall in will be plotted against each other. Scatterplots will be produced combining all visits on the same plot. In addition, the number of observations and Spearman's rank correlation coefficient and Pearson correlation coefficient with corresponding 95% CI will be computed and presented on the scatterplot.

The mean daily frequency of moderate to severe HFs (morning and evening diary) and mean daily frequency of mild, moderate, and severe HFs (morning and evening diary) as well as the change from baseline values will be analyzed using descriptive statistics by study treatment and week. The change from baseline over time by study treatment will be shown using line plots for means and 95% CI.

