6.4 APPENDIX 4: Identification of Intercurrent Events

6.4.1 Premature discontinuation of study treatment

Participants who prematurely discontinue study treatment also withdrawal from study participation at the same time. No further study procedures (except for the safety follow-up visit) will be taken including PSG assessments.

Participants will likely not have a PSG assessment after discontinue study treatment. Therefore, for the identification of the ICE premature discontinuation of study treatment at week 4 and week 12, visit day 30 and day 86 will be used as the PSG assessment day respectively.

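### The hot-flash/WASO correlations are not specified by treatment, and their weekly pairing window runs mostly past on-schedule Week 4 PSG nights and loses on-schedule Week 12 pairs

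*SAP*

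**What the plan says.** SAP 4.4.3 plans scatterplots of four mean daily hot-flash frequencies (night-time only, or day and night; with or without mild flashes) against PSG WASO. Each is drawn for actual values, change and percent change. WASO is the visit value of SAP 4.2.1, normally the mean of two nights. The hot-flash side is a study-week mean: "The mean daily HFs for the same week the week 4 and week 12/EoT PSG assessments fall in will be plotted against each other". On pooling, the SAP says "Scatterplots will be produced combining all visits on the same plot", with Spearman and Pearson coefficients and 95% CIs on the plot. Treatment is not mentioned there, whereas the paragraph that follows, on descriptive hot-flash summaries, asks for results by arm and week.

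The timing rules are spread over several sections:

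- SAP 4.1.2, study week: "This would therefore calculate study day 1 to 7 as study week 0", and "day 29 and day 85 with a plus 7-day visit window are specified for week 4 and 12 respectively".
- SAP 6.4.1, nominal PSG day when none is available: "visit day 30 and day 86 will be used as the PSG assessment day respectively".
- SAP 4.4.3, diary day: "Therefore, a diary day consists of the evening entry and the morning entry of the subsequent day".
- SAP 4.4.3, completeness: "A minimum of 4 days should be available within a study week for the derivation of mean daily frequency"; otherwise the week is missing.
- Protocol 8.2.2.2: the hot-flash diary runs until EoT. Footnote b of the Schedule of Activities puts EoT assessments (other than the safety and PK sample) on the morning after the second PSG night.

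For the sleep diary, SAP 4.4.2 adds a summary restricted to the PSG nights: "In addition, the mean daily value from the PSG nights will be summarized descriptively by study treatment and week". SAP 4.6.3 does the same for Sleepiz One+. Nothing similar is planned for hot flashes.

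**The concern.** The exploratory objective is the relationship between hot flashes and PSG-measured sleep disturbance. The protocol expects the drug to act on both (2.3.2) and notes that night-time vasomotor symptoms do not fully explain menopausal sleep disturbance (2.2). If elinzanetant lowers both variables, a coefficient taken across arms is positive even when the two are unrelated within each arm.

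The second issue is which hot-flash days are set against WASO. A window that starts on the PSG visit day describes mainly the days after the measured nights, and at the last visit those days are never recorded. At stake are how the exploratory result is read and how many Week 12 pairs contribute to it.

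**Working it through.** **1. Study weeks.** The formula itself did not come through in the text available, so I inferred week = CEIL(day/7) - 1. It reproduces the SAP's stated anchors: days 1-7 give week 0, day 29 gives week 4 and day 85 gives week 12. Hence week 4 is days 29-35 and week 12 is days 85-91. From SAP 6.4.1, I take on-schedule PSG nights as 29-30 and 85-86. By the diary-day definition, the night of day d belongs to diary day d.

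**2. Week 4.** Diary days in the paired week, by first PSG night within the +7-day window:

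| First night | Before | PSG nights | After |
|---|---|---|---|
| 29 | 0 | 2 | 5 |
| 30 | 1 | 2 | 4 |
| 31 | 2 | 2 | 3 |
| 32 | 3 | 2 | 2 |
| 33 | 4 | 2 | 1 |
| 34 | 5 | 2 | 0 |
| 35 (straddles weeks 4 and 5; week 4 shown) | 6 | 1 | 0 |
| 36 (falls in week 5) | 0 | 2 | 5 |

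A majority of days after the PSG (4 or more of 7) occurs for first nights on day 29, 30 or 36 only.

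**3. Week 12.** The diary ends the morning after night 2, so no diary day follows the PSG:

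| First night | Diary days available | Minimum of 4 met? |
|---|---|---|
| 85 | 2 | No |
| 86 | 3 | No |
| 87 | 4 | Yes, if none is missed |
| 88 | 5 | Yes |
| 89 | 6 | Yes |
| 90 | 7 | Yes |
| 91 (straddles weeks 12 and 13; week 12 shown) | 7 | Yes |
| 92 (falls in week 13) | 2 | No |

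An on-schedule participant has no Week 12 hot-flash mean and drops out of the plot; PSGs scheduled later in the window supply the Week 12 points.

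**4. Arm mixing.** With 1:1 allocation, within-arm correlation r_w, and arm differences dH (hot flashes) and dW (WASO) in within-arm SD units:

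pooled r = (r_w + dH·dW/4) / √[(1 + dH²/4)(1 + dW²/4)]

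The documents give no effect size for either variable. As an illustration only, set dW = 14.7/33.2 = 0.44, borrowing the planned CI half-width and SD from SAP section 5. With r_w = 0:

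- dH = 0.5: 0.0554/1.056 = 0.05
- dH = 1.0: 0.1107/1.145 = 0.10
- dH = 1.5: 0.1661/1.280 = 0.13

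Over a wider assumed grid (dH 0.4 to 1.2, dW 0.2 to 0.8), a within-arm 0 becomes 0.02 to 0.19, and a within-arm 0.30 becomes 0.31 to 0.43.

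**5. Alternative window.** The 7 diary days ending on the last PSG night are days 24-30 and 80-86 on schedule. Each has 5 days before, 2 PSG nights and 0 after, so all 7 can be collected at both visits.

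**The case against.** The strongest reply is that the SAP is silent on arms and does not order them pooled. SAP 4.1 has a general rule that summaries are given by treatment where appropriate, and the SAP introduction places figure specifications in a separate document. A reader might infer an instruction to merge the arms; the text supports only the absence of a commitment to split them.

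The distortion is also small against sampling error: with 70 participants at one visit, the 95% range around zero is about ±tanh(1.96/√67) = ±0.235. A reader might infer that the hot-flash relationship cannot be told apart from the treatment effect. An induced 0.05 to 0.13 does not support that, and 14.7 minutes is a CI half-width, not an expected effect.

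On timing, a reader might infer that the hot-flash week falls mostly after the PSG at both visits. It does so only at Week 4 and only for some start days; at Week 12 the fault is lost pairs. Nor are same-night counts skipped: they are normally 2 of the 7 days averaged, so they are diluted. And SAP 4.4.2 and 4.6.3 only summarise PSG-night values; they do not correlate them with PSG WASO.

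Finally, weekly means are less noisy than two-night counts, no hypothesis is tested, and the extra analyses could be run later on the same data. All of this limits the point. None of it restores the on-schedule Week 12 pairs or commits the SAP to a treatment-adjusted coefficient.

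**Conclusion.** The point holds as a minor improvement to an exploratory analysis. The correlations are not specified by or adjusted for treatment, which can add about 0.05 to 0.13 to a within-arm correlation of zero under assumed effects. The window is the clearer defect: on schedule, 5 of 7 Week 4 diary days follow the PSG, and Week 12 has 2 diary days against a minimum of 4. PSG-night hot flashes are never isolated.

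The timing results rest on the inferred week formula and on day 29/85 being PSG night 1. If the visit day were instead the morning after night 2, Week 4 nights 27-28 would fall in week 3 with no later days, and Week 12 nights 83-84 would close week 11 (days 78-84) with a full diary week. For the combined day-and-night frequencies, SAP 4.4.3 sets week 0 to diary days 2-8. If that shift carries forward, week 4 becomes days 30-36 and leaves out nominal night 1; the text does not say. How many PSGs will be on schedule is unknown. The primary WASO analysis is unaffected.

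**What to change.** Amend SAP 4.4.3 in three places:

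- **Arms.** Mark treatment on the plots. Give the correlations by arm or as a partial correlation adjusted for treatment, and keep the pooled coefficient beside them.
- **Same nights.** Add the mean night-time hot-flash count from the two PSG nights (the morning entries after each) paired with WASO from those nights.
- **Weekly window.** Use the 7 diary days ending on the last PSG night. SAP 6.4.2 already uses this window for treatment intake.

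The cost is a few SAP sentences and some extra figures. No new data are needed, and protocol 9.3.4 leaves exploratory analyses to the SAP. The price is precision. At about 35 per arm, an illustrative r of 0.30 has a 95% CI of about -0.04 to 0.58, against 0.07 to 0.50 for 70 pooled. Two-night counts are also noisier than weekly means. For those reasons keep both the pooled and by-arm coefficients, and both the weekly and same-night pairings.

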5.1 Inclusion Criteria

Participants are eligible to be included in the study only if all the following criteria apply:

Age

1. Females aged 40 to 65 years, inclusive, at signing of informed consent.

21 SEP 2023 Page: 25 of 73

Type of Participant and Disease Characteristics

2. Being in the post-menopausal period, defined as: serum FSH levels >40 mIU/mL and a serum estradiol concentration of <30 pg/mL at screening,

AND

Hysterectomy performed at least 6 weeks prior to screening.

3. Experiencing VMS associated with menopause, defined as:

Participant has completed HFDD for at least 11 days during the 2 weeks prior to the respective eligibility check, and during this period participant has recorded a weekly average of at least 20 moderate or severe HF (including night-time HF).

- 4. The participant's self-reported sleep history includes ongoing sleep disturbances associated with menopause characterized by waking up at night and/or poor quality of sleep.
- 5. The participant's self-reported ongoing sleep disturbances cause distress or impairment in social, occupational, or other important areas of functioning.
- 6. WASO of 30 minutes or more (mean of 2 screening PSGs with neither of the 2 nights <20 min).
- 7. The participant's self-reported time in bed between 6 and 9 hours.
- 8. The participant's self-reported bedtime is usually between 21.00 and 24.00 hours and it does not vary by more than ± 2 hours.
- 9. Negative urine pregnancy test at screening.
- 10. BMI between 18 and 38 kg/m² at screening.

Informed Consent

11. Capable of giving signed informed consent as described in Section 10.1.3 which includes compliance with the requirements and restrictions listed in the ICF and in this protocol.

Additional criteria

- 12. Normal breast cancer screening result available prior to start of treatment in line with the method and frequency recommended in the respective country. The time elapsed since the last screening examination should be sufficiently short that no further routine screening examination needs to be scheduled during the course of the study. ²
- 13. In individuals with a cervix: normal cervical cancer screening result available prior to start of treatment in line with the method and frequency recommended in the respective country. The time elapsed since the last screening examination should be sufficiently short that no further routine screening examination needs to be scheduled during the course of the study.

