1	night 'Study medication intake documentation' data at week 12 if eCRF data indicate that subject received treatment for calculation of treatment compliance using eDiary data (Section 4.5.1).	Rules added based on blinded data review.
1	2) Additional analyses on hot flash daily diary data were added (Section 4.4.3)	Changes made based on TFL specification and blinded review of tables and figures.
1	3) Individual participant presentations in Section 4.5.3.2 were modified	Figures and Listing were modified to be consistent with advice from OASIS pre-NDA meeting with FDA.
1	4) Modified to take average value if more than 1 measurement is available on the same date for vital signs (Section 4.5.3.3).	Rules added based on blinded data review.

Version 2.0 Page: 6 of 57

5) For Sleepiz One+ data, added if recording started on or before 11am then date of observation will be the day before, added rules to exclude data recorded after end of treatment, and added analysis using only nights with GSD ≥ 4 hours (Section 4.6.3)	Rules added based on blinded data review.
6) Modified summary of hysterectomy to summary of oophorectomy (Section 6.1.3)	Changes made based blinded review of tables and figures.
7) Added summary of relevant prior and concomitant procedures (Section 6.1.6)	Added based on blinded data review.
B) Modified definition of average awakening from Sleepiz One+ data (Section 6.2.2)	Modified to reflect the data based on blinded data review.
Preliminary list of prohibited therapies was added. Two tables were added to allow specification of prohibited hormonal therapies and prohibited concomitant medication impacting PK by drug groupings, and one table to allow specification of prohibited concomitant medications potentially confounding efficacy by drug names (Section 6.3).	Added based on blinded data review.
bleeding" typo corrected, deleted duplicate term and added new term "PT Unexpected vaginal bleeding on hormonal IUD" (Section 6.5).	Update of applicable coding conditions.

Version 2.0 Page: 7 of 57

List of Abbreviations and Definitions of Terms

AE(s) Adverse event(s)

AESI Adverse event of special interest

AHI Apnea hypopnea index / Respiratory Irregularity Index (for Sleepiz One+)

ALT Alanine aminotransferase AP Alkaline phosphatase AST Aspartate aminotransferase

BMI Body mass index
CK Creatinine kinase
CV Coefficient of variation
eCRF(s) Electronic case report form(s)

eC-SSRS Electronic Columbia-Suicide Severity Rating Scale

eDiary Electonic diary

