4.4 Exploratory/Other Endpoints Analysis

For all exploratory endpoints, the ICEs will be handled according to the treatment policy. No missing data imputation is planned for these endpoints. Analyses will be performed using the FAS.

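### Minor, exploratory: SAP 4.4.3 pools week 4 and week 12/EoT points in one hot-flash-versus-WASO correlation and prints a 95% CI, with no allowance for participants who contribute two points

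*SAP*

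**What the plan says.** SAP Table 1-1 lists the relationship between HFs and PSG-determined sleep disturbance as an exploratory objective. SAP 4.4.3 addresses it with scatterplots of four HF measures against WASO, "produced separately for the actual values, change from baseline and percent change from baseline". That makes 4 × 3 = 12 plots.

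On the visits used, it says: "The mean daily HFs for the same week the week 4 and week 12/EoT PSG assessments fall in will be plotted against each other." It then says: "Scatterplots will be produced combining all visits on the same plot." The number of observations, Spearman's coefficient and the "Pearson correlation coefficient with corresponding 95% CI will be computed and presented on the scatterplot". No CI method is named, and nothing is said about two points from one participant.

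Three other rules bear on how many points there will be:

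- SAP 4.4: "For all exploratory endpoints, the ICEs will be handled according to the treatment policy." Points are therefore not removed because of an intercurrent event.
- SAP 4.4.3: a weekly HF mean needs at least 4 available diary days in that study week; otherwise it is missing.
- SAP 4.1.2: study days 1 to 7 are week 0, so week 12 is days 85 to 91.

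For the HF baseline: "The baseline value will be calculated similarly using all available days with data during the 14 days prior to starting treatment." Each participant has one baseline value, used for both on-treatment visits.

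**The concern.** A correlation CI computed from the number of points treats every point as independent. Two points from the same woman are not independent if women with many hot flashes at week 4 still have many at week 12 and women with high WASO keep high WASO. The pooled coefficient then varies more than the formula assumes, and the printed interval is too short. On the change and percent-change scales, subtracting or dividing by the same baseline at both visits creates this dependence even if the on-treatment values do not persist at all.

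The primary MMRM models the within-subject covariance of WASO at these same two visits (SAP 4.2.2), whereas the correlation analysis states no counterpart. What is at stake is limited: these are the planned estimates of the HF–WASO association, and a CI that counts points would show somewhat more precision than the data hold.

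**Working it through.** **The plan's own figure.** The documents give no precision figure for the correlation. The only one is for the week 4 WASO difference (SAP 5): half width 14.7 min at 35 per arm with SD 33.2. It reproduces: t(0.95, 68) × 33.2 × √(2/35) = 13.23, and multiplying by √(χ²(0.90, 68)/68) gives 14.65. From it I take only the 70 planned evaluable participants.

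**How many second points?** The HFDD runs until EoT (Protocol 8.2.2.2), and EoT assessments take place on the morning after the second PSG night (Protocol Table 1-2, footnote b). T3 is day 85 with a window of +7 days, and SAP 6.4 uses day 86 when the last PSG night is missing. With PSG nights on days 85 and 86, only diary days 85 and 86 fall in week 12. Two days is below the minimum of four, so that participant has no week 12 HF value and no week 12 point. Four days (85 to 88) need a second PSG night on day 88 or later. The share of participants with two points therefore cannot be read from the documents. I use 70 (all) and 35 (half) as illustrations.

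**Formula.** Take 70 week 4 points, of which P participants also have a second point, so n = 70 + P. At true r = 0, with within-person correlations ρ_HF and ρ_WASO between visits, the standard error exceeds the point-counting one by

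f = √(1 + 2P·ρ_HF·ρ_WASO / n),

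and a nominal 95% Fisher-z interval covers 2Φ(1.96/f) − 1. If either correlation is 0, f = 1 and coverage stays at 95%.

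**Actual values** (the ρ values are assumptions; the documents give none):

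| ρ_HF / ρ_WASO | P = 70: f | coverage | P = 35: f | coverage |
|---|---|---|---|---|
| 0 / 0.7 | 1.00 | 95.0% | 1.00 | 95.0% |
| 0.3 / 0.3 | 1.04 | 94.0% | 1.03 | 94.3% |
| 0.5 / 0.5 | 1.12 | 92.0% | 1.08 | 93.0% |
| 0.8 / 0.8 | 1.28 | 87.4% | 1.19 | 89.9% |

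Example: 0.8/0.8 with P = 35 gives f = √(1 + 70 × 0.64/105) = 1.19. Simulations (20,000 runs, bivariate normal) agree: 93.9%, 92.2% and 87.4% for P = 70, and 94.0%, 93.2% and 89.8% for P = 35, at 0.3, 0.5 and 0.8.

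**Change from baseline, no persistence.** Let v be the baseline variance divided by the on-treatment variance. Two changes that share a baseline correlate at v/(1 + v), which is 0.33, 0.50 and 0.60 for v = 0.5, 1 and 1.5. Putting these in for both variables:

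| v | P = 70 | P = 35 |
|---|---|---|
| 0.5 | 93.7% | 94.1% |
| 1 | 92.0% | 93.0% |
| 1.5 | 90.7% | 92.2% |

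Simulation gives 93.9%, 92.1% and 90.8% for P = 70, and 94.1%, 93.4% and 92.1% for P = 35. The ratio v is unknown. The HF baseline averages up to 14 days against 7-day weeks, and baseline WASO is cut off from below by inclusion criterion 6 (Protocol 5.1). Percent change shares the baseline in the same way.

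**Widths at r = 0.** The point-counting half width is tanh(1.96/√137) = 0.166 with 140 points. At 0.8/0.8 the half width needed is tanh(1.28 × 1.96/√137) = 0.21.

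**The case against.** The strongest objection is that no defective interval has been shown. SAP 1 puts figure specifications in a separate document, and item 12 of the version history ties the HFDD additions to the TFL specification. A participant-level method may be set there. This stands: what can be shown is that 4.4.3 fixes the pooling and is silent on the CI.

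The sizes also rest on assumed persistence and variance ratios, and the simulations use one homogeneous population although the trial has two arms. That stands too. At low persistence, or if only one variable persists, the loss is negligible.

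A reader might infer from the treatment-policy rule that most participants will contribute two points, so that the full-pairs figures are what to expect. The documents do not support this. That rule only stops points being discarded. The 4-day minimum, the week 12 definition and the end of the diary at EoT can leave a participant who is exactly on schedule without a week 12 HF value. Participants who stop early have no later PSG (SAP 6.4.1).

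A reader might also take the pooling of all visits to include baseline, which would give three points each. The preceding sentence in 4.4.3 names only week 4 and week 12/EoT.

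Finally, the output is a figure annotation and no hypothesis is tested (SAP 2). That sets the grade but does not remove the gap: an interval labelled 95% should be close to it, and printing the number of observations does not correct it.

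**Conclusion.** The point holds as a minor one. Followed with the ordinary correlation CI, SAP 4.4.3 gives intervals that are too narrow when both variables persist within a person, and on the change and percent-change plots also through the shared baseline. With 70 full pairs, coverage is about 94%, 92% and 87–88% at persistence 0.3, 0.5 and 0.8 in both variables, and about 91% to 94% for change from baseline without persistence. These figures are an upper bound on the shortfall for the assumed persistence and variance ratio, because the share of participants with two points is unknown. With 35 second points they become about 94%, 93% and 90%, and about 92% to 94%. All assume a Fisher-z interval on the number of points and r = 0. Primary and secondary analyses are untouched.

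**What to change.** Keep the combined plot and add to SAP 4.4.3 one of two rules. Either give coefficients and CIs per visit, so that each participant supplies one point, or take the CI of the pooled coefficient from a bootstrap that resamples participants. In both cases print the number of participants beside the number of observations. If the figure specifications already contain such a rule, a cross-reference is enough.

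The cost is minor programming and somewhat wider intervals. Per visit, the half width at r = 0 is tanh(1.96/√67) = 0.235 with 70 participants, against 0.166 for 140 points counted as independent. A week 12 plot with 35 participants would have tanh(1.96/√32) = 0.333. The participant bootstrap is less costly: with 70 full pairs its mean half width runs from 0.168 (0.3/0.3) to 0.205 (0.8/0.8). Its percentile coverage is 93.6% to 94.2%, so it gains nothing at low persistence and matters only when persistence is moderate or high.
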